## Figure 2. Overview of the VTE Reporting Periods

# 9.2.2. CV and Malignancy Reporting Periods

A 105-month **observation period** will begin 01 April 2016 and end 31 December 2024. An 81-month **indexing period** will begin 01 April 2017 (i.e., the earliest date of the full distribution of the original aRMM materials for a country and indication [Sweden, RA]), end 31 December 2023, and be used to identify patients with  $\geq$ 1 tofacitinib prescription dispensing. Additionally, for some analyses, the indexing period will be split into the following 3 periods:

• **Reporting Period 1**, which will cover the up-to-51-month period after the initial distribution of the aRMM materials but *prior to* the PRAC/CHMP's notification of an increased risk of CV-related outcomes and malignancy-related outcomes among patients already at high risk (01 April 2017 through 30 June 2021, to allow for dissemination of DHPC letters);

**Note:** Hungary will not have a **Reporting Period 1** for PsA and UC because it has yet to receive full reimbursement for PsA and UC (anticipated Q1 2023).

The anticipated start date of distribution of the 2021 signal evaluation procedure aRMM materials for most countries is some time in Q4 2021. Therefore, ranges have been included

for the start and end dates of the CV and Malignancy Reporting Periods 2 and 3 assuming that the 2021 signal evaluation procedure aRMM materials are distributed at the beginning of Q4 (01 Oct 2021) and at the end of Q4 (31 Dec 2021). Thus, the CV and Malignancy Reporting Period 2 will start 01 July 2021 and end either as early as 31 March 2022 (lasting 9 months) or as late as 30 June 2022 (lasting 12 months). Accordingly, the CV and Malignancy Reporting Period 3 will start either as early as 01 April 2022 or as late as 01 July 2022 and end 31 December 2023, lasting either 21 months or 18 months, respectively.

• **Reporting Period 2**, which will cover the 9-12 month period of and after the PRAC/CHMP's notification of restrictions on use in the context of increased risk of CV-related outcomes and malignancy-related outcomes, through initial distribution and uptake of the 2021 signal evaluation procedure aRMM materials (01 July 2021 through Q1/Q2 2022);

**Note:** Hungary will not have a **Reporting Period 2** for PsA and UC because the anticipated distribution date for the 2021 signal evaluation procedure aRMM materials (Q4 2021) will occur prior to PsA and UC receiving full reimbursement (anticipated Q1 2023). Additionally, **Reporting Period 2** for the Netherlands will be adjusted in the statistical analysis plan (SAP) to reflect distribution and uptake of the 2021 signal evaluation procedure aRMM materials in Q1 2022.

• **Reporting Period 3,** which will cover the 18-21-month period *after* the period of initial distribution and uptake of the 2021 signal evaluation procedure aRMM materials (Q2/Q3 2022 through 31 December 2023).

**Note: Reporting Period 3** for the Netherlands will be adjusted in the SAP to reflect distribution and uptake of the 2021 signal evaluation procedure aRMM materials in Q1 2022.

See Figure 3 for an overview of the CV and Malignancy Reporting Periods 1-3.

## Figure 3. Overview of the CV and Malignancy Reporting Periods

**Note:** If, at the end of CV and Malignancy Reporting Period 3, a minimum of 100 tofacitinib patients have not been accrued for a specific approved indication-country combination (e.g., UC in Sweden), then CV and Malignancy Reporting Period 3 will be extended as the data are available. For example, if market uptake is slower than expected, then CV and Malignancy Reporting Period 3 will be extended by 12 months or longer if necessary.

### 9.2.3. Patient-specific study period

Patients will be included in the study analyses if they have  $\geq 1$  tofacitinib prescription dispensing during the indexing period and meet the study inclusion and exclusion criteria (described in Section 9.2.4 [Inclusion criteria] and 9.2.5 [Exclusion criteria], respectively). The date of a patient's first tofacitinib prescription dispensing during the indexing period will be considered the patient's **index date**. Each patient will have their own unique **study period** (based on their index date), consisting of a 12-month **baseline period** and a 12-month **follow-up period** (Figure 4).

# Figure 4. Example index tofacitinib dispensing and patient-specific study period against the VTE Reporting Periods

The 12-month **baseline period** will immediately precede the patient's index date and will be used to ascertain indication (including off-label indications), comorbidities, prior and current medications, potential contraindicated use of tofacitinib, VTE risk factors, use in patients aged 65 years and older, CV risk factors, malignancy risk factors, and whether there is evidence that prescribers are following the recommended screenings in the aRMM materials that should occur *prior to* initiation of tofacitinib.

The 12-month **follow-up period** will begin on the patient's index date and will be used to ascertain comorbidities, comedications, compliance to the recommended posology per indication (ADD) and duration of tofacitinib treatment, potential contraindicated use of tofacitinib, VTE risk factors, CV risk factors, malignancy risk factors, use with concomitant medications not compatible with tofacitinib, and whether there is evidence that prescribers are following the recommended monitoring in the aRMM materials that should occur *after* initiation of tofacitinib.

### 9.2.4. Inclusion criteria

Patients must meet all of the following inclusion criteria to be eligible for inclusion in the study:

- 1. Have ≥1 prescription dispensing of tofacitinib (Anatomical Therapeutic Chemical [ATC] code L04AA29) in the selected databases during the indexing period;
- 2. Have 12 months of available medical history *prior to* the index tofacitinib dispensing; and
- 3. Have 12 months of available medical history *after* the index tofacitinib dispensing.

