The sub-objective that evaluates "prescribers' adherence to the tofacitinib aRMMs, specifically, compliance to patient screening and laboratory monitoring prior to and during tofacitinib treatment" will *not* be assessed in Sweden because the Swedish national health registers do not capture the laboratory tests of interest. In GKV claims, it may not be possible to differentiate an absolute lymphocyte count (ALC) laboratory test from an absolute neutrophil count (ANC) laboratory test, or an alanine aminotransferase (ALT) laboratory test from an aspartate aminotransferase (AST) laboratory test. In the PHARMO Database Network, tuberculosis (TB) screening and viral hepatitis B and C testing are not captured.

**Study design:** This will be a descriptive drug utilisation study using secondary data collected from databases in Sweden, Hungary, the Netherlands, and Germany. The study observation period will be 01 April 2016 through 31 December 2024. All results will be stratified by study country and approved indication (i.e., RA, PsA, and UC).

**Population:** Patients will be included in the study if they have  $\geq 1$  prescription dispensing of tofacitinib during the indexing period, 12 months of available medical history before and 12 months after the index tofacitinib dispensing, and 0 prescription dispensings of tofacitinib in the 12 months prior to the indexing period.

**Variables:** Demographic characteristics (age, sex), diagnoses (indication [including off-label indications], comorbidities, contraindicated use, VTE risk factors, CV risk factors, malignancy risk factors), patients 65 years and older with no alternative treatments prior to initiation of tofacitinib, prior and current medications, procedures (including screening and monitoring tests), ADD, and duration of tofacitinib therapy will be examined.

**Data sources:** This study will use the Swedish national health registers: National Patient Register (NPR), the Swedish Prescribed Drug Register (PDR), the Swedish Medical Birth Register (MBR), the Swedish National Cancer Registry (NCR), and the Swedish Cause of Death Register; in Hungary, the National Health Insurance Fund Administration (NHIFA), an administrative claims database; in the Netherlands, the PHARMO Database Network, a population-based network of electronic healthcare databases; and in Germany, GKV claims, an administrative claims database.

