In May 2019, the EC requested a reassessment of the benefit-risk of tofacitinib pursuant to Article 20 of Regulation (EC) No 726/2004 due to a signal for increased risks of pulmonary embolism and mortality arising in an ongoing Pfizer-sponsored Phase 3b/4 safety study (A3921133) designed to evaluate the risk of malignancy and major adverse cardiac events in RA patients aged 50 years and older who had at least one cardiovascular (CV) risk factor. In November 2019, the Committee on Human Medicinal Products (CHMP) concluded, based on a recommendation from the Pharmacovigilance Risk Assessment Committee (PRAC), that patients treated with tofacitinib are at increased risk of venous thromboembolism (VTE) events, both for deep venous thrombosis as well as pulmonary embolism, especially in patients with risk factors for VTE. The PRAC further concluded that the risk of VTE events is dose-dependent. To minimise this risk, the PRAC recommended that warnings be added to the Summary of Product Characteristics (SmPC) regarding the increased risk of VTE observed in patients taking tofacitinib, especially for patients with known risk factors for VTE. The PRAC also recommended that treatment with tofacitinib be discontinued in patients with suspected VTE and that tofacitinib 10 mg BID for maintenance treatment is not recommended in patients with UC who have known VTE risk factors unless there is no suitable alternative treatment available. Clarifications on the posology were also added, particularly for UC patients in maintenance. Specifically, some patients (i.e., patients who failed to respond to alternative treatment options for UC such as tumour necrosis factor [TNF] inhibitor treatment) who had a reduction in response to 5 mg BID maintenance treatment may benefit from an increase in maintenance dose to 10 mg BID; for these patients, the presence of known risk factors for VTE should be considered. However, tofacitinib 10 mg BID for maintenance treatment should be used for the shortest duration possible.

The PRAC also concluded that, based on the interim analyses of Study A3921133, there is a potential increased risk of mortality. This was partly driven by an increased risk of serious infections among patients 65 years and older. As such, tofacitinib should be considered

among patients 65 years and older only if no suitable alternative treatment is available. These conclusions and revisions to the SmPC were approved by the EC on 31 January 2020.

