Subsequently, in June 2021, as a result of a signal evaluation procedure (EPITT number 19382) to assess the increased incidence rate of major adverse cardiovascular events (MACE) and malignancies excluding non-melanoma skin cancer (NMSC) in patients treated with tofacitinib for RA, the European Medicines Agency (EMA) concluded that myocardial infarction (MI), lung cancer, and lymphoma were important identified risks. To minimise these risks, and the important potential risk of MACE and malignancies excluding NMSC, the EMA recommended that the SmPC be updated to include restrictions on use of tofacitinib in patients over 65 years of age, patients who are current or past smokers, patients with other CV risk factors, and patients with other malignancy risk factors (e.g., current malignancy or history of malignancy other than a successfully treated NMSC). In these patients, tofacitinib should only be used if no suitable treatment alternatives are available.

In conjunction with the initial authorisation in March 2017, to minimise important potential and identified risks associated with the use of tofacitinib and to continue to monitor important potential and identified risks, the Marketing Authorisation Holder (MAH) implemented an educational program designed to increase awareness of the risks of tofacitinib in each member state of the European Union (EU). This program consists of routine (i.e., SmPC and patient package insert) and additional risk minimisation measures (aRMMs; i.e., a prescriber brochure, checklists for treatment initiation and treatment maintenance, and a patient alert card to distribute to patients). There is also a website where healthcare professionals (HCPs) can access the aRMM materials.

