#### Figure 1. Overview of the study observation period

### 9.2.1. VTE Reporting Periods

A 105-month **observation period** will begin 01 April 2016 and end 31 December 2024. An 81-month **indexing period** will begin 01 April 2017 (i.e., the earliest date of the full distribution of the original aRMM materials for a country and indication [Sweden, RA]), end 31 December 2023, and be used to identify patients with  $\geq$ 1 tofacitinib prescription dispensing. Additionally, for some analyses, the indexing period will be split into the following 3 periods:

• **Reporting Period 1**, which will cover the up-to-26-month period after the initial distribution of the aRMM materials but *prior to* the PRAC/CHMP's notification of an increased risk of VTE among patients already at high risk (01 April 2017 through 31 May 2019, to allow for dissemination of DHPC letters following announcement of the provisional measures);

**Note:** Hungary will not have a **Reporting Period 1** because it received full reimbursement for RA in May 2019 and has yet to receive full reimbursement for PsA and UC (anticipated Q1 2023).

• **Reporting Period 2**, which will cover the 16-month period of and after the PRAC/CHMP's notification of an increased risk of VTE and mortality, through initial distribution and uptake of the 2019 Article 20 referral aRMM materials (1 June 2019 through 30 September 2020); and

**Note:** Hungary will not have a **Reporting Period 2** for PsA and UC because the September 2020 distribution date for the 2019 Article 20 referral aRMM materials in Hungary occurred prior to PsA and UC receiving full reimbursement (anticipated Q1 2023). Additionally, **Reporting Period 2** for RA in Hungary will only allow for <1 month of uptake of the 2019 Article 20 referral aRMM materials (which were distributed starting September 2020), in comparison to the approximate 6-7 month uptake of the

2019 Article 20 referral aRMM materials allowed for Sweden (which were distributed starting March 2020).

• **Reporting Period 3,** which will cover the 39-month period *after* the period of initial distribution and uptake of the 2019 Article 20 referral aRMM materials (1 October 2020 through 31 December 2023).

See Figure 2 for an overview of the VTE Reporting Periods 1-3.

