Sec	tion 7: Bias	Yes	No	N/ A	Section Number
7.3	Does the protocol address information bias? (e.g. misclassification of exposure and outcomes, time- related bias)	$\boxtimes$			9.9

Comments:

Given the descriptive nature of the study and a lack of control groups, the study is not concerned with the impact of confounding or selection bias.

Sect	ion 8: Effect measure modification	Yes	No	N/ A	Section Number
8.1	Does the protocol address effect modifiers? (e.g. collection of data on known effect modifiers, sub- group analyses, anticipated direction of effect)			$\boxtimes$	n/a

Comments:

Sec	tion 9: Data sources	Yes	No	N/ A	Section Number
9.1	Does the protocol describe the data source(s) used in the study for the ascertainment of:				
	9.1.1 Exposure? (e.g. pharmacy dispensing, general practice prescribing, claims data, self-report, face-to-face interview)				9.4
	9.1.2 Outcomes? (e.g. clinical records, laboratory markers or values, claims data, self-report, patient interview including scales and questionnaires, vital statistics)				9.4
	9.1.3 Covariates and other characteristics?	$\square$			9.4
9.2	Does the protocol describe the information available from the data source(s) on:				
	9.2.1 Exposure? (e.g. date of dispensing, drug quantity, dose, number of days of supply prescription, daily dosage, prescriber)				9.4
	9.2.2 Outcomes? (e.g. date of occurrence, multiple event, severity measures related to event)	$\boxtimes$			9.4
	9.2.3 Covariates and other characteristics? (e.g. age, sex, clinical and drug use history, co- morbidity, co-medications, lifestyle)				9.4
9.3	Is a coding system described for:				
	9.3.1 Exposure? (e.g. WHO Drug Dictionary, Anatomical Therapeutic Chemical (ATC) Classification System)				9.4
	9.3.2 Outcomes? (e.g. International Classification of Diseases (ICD), Medical Dictionary for Regulatory Activities (MedDRA))				9.4
	9.3.3 Covariates and other characteristics?	$\boxtimes$			9.4

Sec	tion 9: Data sources	Yes	No	N/ A	Section Number
9.4	Is a linkage method between data sources described? (e.g. based on a unique identifier or other)	$\boxtimes$			9.4

Comments:

Section 10: Analysis plan	Yes	No	N/ A	Section Number
10.1 Are the statistical methods and the reason for their choice described?	$\boxtimes$			9.7
10.2 Is study size and/or statistical precision estimated?	$\boxtimes$			9.5
10.3 Are descriptive analyses included?	$\square$			9.7
10.4 Are stratified analyses included?	$\boxtimes$			9.7

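### Requiring 12 months of data after index drops initiators who die or leave within a year, even from outcomes already fixed at initiation

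*Protocol*

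**What the plan says.** Section 9.2.4 states that "Patients must meet all of the following inclusion criteria to be eligible for inclusion in the study", and the third criterion is "Have 12 months of available medical history *after* the index tofacitinib dispensing". The Abstract repeats it: "12 months of available medical history before and 12 months after the index tofacitinib dispensing". Section 9.2.3 admits to the study analyses only patients who meet these criteria, so the rule is global.

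Three other parts of the protocol bear on it.

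- **Calendar.** Section 9.2.1 says "A 105-month observation period will begin 01 April 2016 and end 31 December 2024", and indexing closes on 31 December 2023.
- **When outcomes are ascertained.** Section 9.2.3 says "The 12-month baseline period will immediately precede the patient's index date". It uses that window for indication, risk factors, age 65 or over, contraindications and pre-initiation screening.
- **Bias.** The comment under Section 7 of the Annex 2 checklist says that, because the study is descriptive and has no control group, "the study is not concerned with the impact of confounding or selection bias". Section 12 of the checklist marks selection bias as not applicable. The limitations in Section 9.9 do not mention this exclusion.

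**The concern.** The criterion selects on something that happens after the prescribing decision under study. A patient who starts tofacitinib and dies, or leaves the data source, in month 5 has a complete baseline record. That patient is still removed from the proportion of initiators with a CV risk factor, with no prior biologic, or with a contraindication.

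This matters because of why the study exists. Section 7 reports that "there is a potential increased risk of mortality" and that "myocardial infarction (MI), lung cancer, and lymphoma were important identified risks". The compliance question is how often tofacitinib is started, or kept going, in patients to whom these warnings apply. If such patients are likelier to be lost within the year, the reported proportions make prescribing look somewhat more compliant than it was.

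The reason given in Annex 2 for setting selection bias aside does not hold. A single proportion needs no comparator to be biased. It is enough that inclusion depends on something related to the characteristic being counted.

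**Working it through.** **1. The plan's own figure.** Section 9.5 uses n = P(1-P)z²/e² with P = 0.50, z = 1.96 and e = 0.10. This gives 0.25 × 3.8416 / 0.01 = 96.04, so 97, rounded up to 100 per indication per country. It reproduces, as do all six rows of Table 5. The target counts eligible patients and is not disputed. It supplies the planned half-width of 10 percentage points.

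**2. What the criterion removes.** The last index date is 31 December 2023 and observation ends on 31 December 2024. In the final report every initiator therefore has 12 calendar months after index, and the criterion can remove only those who die or leave the source. In the interim reports it also screens out late index dates; a limit on the index date would do that without conditioning on survival.

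**3. Effect on a baseline proportion.** Let p be the true share of initiators with the risk factor, d the share of initiators excluded, and RR the ratio of the exclusion probability with the factor to that without it. Then:

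- exclusion without the factor: d0 = d / (p·RR + 1 - p)
- exclusion with the factor: d1 = RR·d0
- reported share = p(1 - d1) / (1 - d)

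Worked case, p = 0.30, d = 0.10, RR = 4: d0 = 0.10/1.9 = 0.0526; d1 = 0.2105; reported share = 0.30 × 0.7895 / 0.90 = 0.2632, which is 3.68 points low.

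The protocol gives none of p, d or RR, so all three are assumptions. Understatement in percentage points:

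| p | RR | d = 1% | d = 5% | d = 10% |
|---|---|---|---|---|
| 0.30 | 2 | 0.16 | 0.85 | 1.79 |
| 0.30 | 4 | 0.33 | 1.75 | 3.68 |
| 0.50 | 2 | 0.17 | 0.88 | 1.85 |
| 0.50 | 4 | 0.30 | 1.58 | 3.33 |

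With RR = 1 the error is zero in every cell.

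**4. Rare contraindicated initiation.** Assume true use of 2%, with 30% of those patients lost against 2% of the others. Reported use = 0.02 × 0.70 / (0.02 × 0.70 + 0.98 × 0.98) = 0.0140 / 0.9744 = 1.4%. The absolute error is small, but the figure is more than a quarter too low.

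**5. Continue or discontinue after a new on-treatment event.** Let f be the share of patients with the event who are excluded, and q the share of those excluded who had discontinued. With an assumed true discontinuation of 40%, the reported value = (0.40 - f·q) / (1 - f).

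- f = 0.10: 33% if q = 1, 44% if q = 0.
- f = 0.20: 25% if q = 1, 50% if q = 0.

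The reported figure can fall on either side of the truth, so the direction is not determined.

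**The case against.** The strongest case against is that the effect is modest and rests on assumed inputs. Against a planned half-width of 10 points, an error of 0.2 to 3.7 points would seldom change a reading. The composites are broad: the VTE list includes age over 50 and hypertension, and the CV list includes diabetes, hypertension and any lipid-lowering dispensing. Nothing in the protocol shows high one-year loss in such groups. Comparisons between reporting periods apply the same rule throughout, so a stable bias largely cancels. Several outcomes do need the year: average daily dose to Week 47, monitoring to day 360, and dispensing after age 65.5. There is also a trap in simply admitting patients who die. Table 3 defines discontinuation as no dispensing in a window after the code, so deaths would be counted as compliance.

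Most of this stands and limits the size of the point. It does not rescue the rule for outcomes fixed at initiation, where the missing year is irrelevant. Monitoring outcomes already carry their own requirement of 6 or 12 months of therapy (Section 9.3.1). Nor does sampling error excuse the bias, which does not shrink with numbers: at 385 patients Table 5 gives a half-width of 5 points.

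Two stronger readings are tempting. A reader might infer that the highest-risk patients are systematically removed and their use certainly under-reported. The protocol does not support this: high-risk patients who survive the year stay in, and leaving a source such as GKV claims may be a change of insurer with no stated link to risk. A reader might also infer that a large fraction of on-treatment VTE, MI or malignancy events disappears. That would need a fatality rate the protocol does not give, and the effect is diluted in composites that also count hypertension, diabetes, hormonal contraceptives or reaching 65.

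The phrase about available history could be taken to mean data up to death. The protocol does not say so, and the four data sources could apply it differently, so clarification is needed either way.

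**Conclusion.** The concern holds as a selection problem of limited size. As written, criterion 3 excludes from every analysis those who die or leave within 12 months, including from outcomes complete at index, and Annex 2 dismisses the issue for a reason that does not apply to a proportion.

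Baseline risk-factor shares are understated by about 0.2 to 3.7 points if 1-10% of initiators are lost and loss is 2-4 times as likely with a risk factor. They are unaffected if loss is unrelated to risk. Rare contraindicated initiation can be understated by more in relative terms. The continue/discontinue proportions may move by 10 to 15 points at the extremes if 20% of patients with an event are excluded and true discontinuation is 40%, in either direction. All these loss rates are assumptions. No conclusion of the study is shown to reverse, and the sample-size target is unaffected. Severity: should-fix.

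**What to change.** 1. Replace criterion 3, in Section 9.2.4 and the Abstract, by an index date at least 12 months before the end of the available data. Keep the 12-month baseline requirement.
2. Report all at-initiation outcomes in every initiator.
3. Follow each patient to the earliest of death, database exit or 12 months, and require full follow-up only for outcomes that need it.
4. For continue/discontinue outcomes, including those after reaching 65, state that absence of dispensing after death or exit is not discontinuation. Show death as its own category where it is recorded: Sweden, Hungary and the Netherlands (Sections 9.4.1 to 9.4.3). Section 9.4.4 does not describe death among the GKV variables but does list time insured, so end of insurance would serve as exit there unless death proves available.
5. Tabulate the number and baseline risk factors of patients who die or leave within 12 months, by country and indication. This replaces the assumed loss rates above with observed ones.
6. Correct the Annex 2 comment and add the point to Section 9.9.

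The cost is an amendment to one criterion and the related definitions. The downside is that variable follow-up must be handled in the post-index outcomes.
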